The diagnosis of superinfections in mechanically ventilated Covid-19 patients

Prospective, observational multicentre study

The inclusion criteria are as follows:

- Age > 18 years
- SARS-CoV-2 PCR positivity in the last 21 days
- Mechanical ventilation for Covid-19 pneumonia
- Presence of lung infiltrations on the chest X-ray or ground glass opacity, crazy paving or lung infiltrations on the chest CT
- Oxygenation disorder according to ARDS definition: $\text{PaO}_2 / \text{FiO}_2 < 300 \text{ mmHg}$ with PEEP at least 5 cmH₂O

The exclusion criteria are as follows:

- Disagreement with the inclusion in the trial

Outcomes

- Primary outcome is incidence and characteristics of superinfections in patients with COVID-19
- Secondary outcome:
 - ◆ Markers of infection / inflammation diagnostic values for the diagnosis of a specific type of superinfection
 - ◆ comparison of the incidence of bacterial and opportunistic superinfections with a historical cohort, where the extension of diagnostics with bronchoalveolar lavage was performed only in patients who did not respond to antibacterial therapy

Informed consent

Considering mechanical ventilation as the inclusion criteria, patients enrolled in this study will not be able to give informed consent. This will be replaced by consent obtained from a doctor independent of the study (at the University Hospital in Brno) or a close relative (at the University Hospital at St. Anne's in Brno), who will assess the risks and benefits of the study for the patient. Patients enrolled in the study are transported from the entire South Moravian region. In terms of their quick enrollment (within 36 hours of admission) and the inability of a close relative to appear in person to sign informed consent, consent to enter the study can be obtained as follows: The doctor will contact the close relative by telephone with two witnesses and the call will be with a loud speaker. After the consent of the close person to enroll the patient in the study, the signature clause will contain the names of the close relative / legal representative and the doctor who enrolled the patient in the study and communicated with the close relative. The telephone number, including the time of the call, as well as the names of both witnesses, including their signatures, will also be recorded. After regaining consciousness, patients will be asked for additional informed consent. If they refuse to participate in the study, the data obtained will not be used for analysis.

Size of the group of patients

The number of patients enrolled in the study depends on the epidemiological situation and the number of admitted patients with severe COVID-19 disease. We expect that the University Hospital at St. Anne's enrolls 75 patients and the University Hospital Brno also enrolls 75 patients. The size of the group is not relevant due to character of the study.

Monitored parameters

Bronchoalveolar lavage (BAL) is the only procedure that differs from standard care. It is usually performed in patients with a suspected lung infection that does not respond to antibiotic therapy. In the study, BAL will be performed early after admission and then in 7-day intervals (± 1 day). This interval can be shortened to a minimum of 3 days if there are signs of a new lung infection.

Basic characteristics of patients in trial

- age, gender
- COVID-19 vaccination and recovery from Covid-19 disease
- severe comorbidities – especially hypertension, diabetes (on PAD / insulin), chronic renal insufficiency, COPD, asthma, chronic heart failure, liver cirrhosis, immunosuppression or chemotherapy, immunodeficiency, cancer
- medication before admission to the ICU:
 - ◆ COVID-19 treatment: antiviral therapy (remdesivir,...), SARS-CoV-2 monoclonal antibodies, corticosteroids (type and total dose in dexamethasone equivalent), immunomodulatory monoclonal antibodies (eg tocilizumab), other drugs used to treat COVID-19
 - ◆ chronically used steroids and other immunosuppressive drugs
 - ◆ antibiotics
- first symptoms of respiratory disease, date of first positive PCR test
- length of UPV, NIV or HFNO before enrollment in the study
- APACHE II and SOFA scores at the day of enrollment in the study
- ClinicalFrailtyScale

Daily monitoring:

- laboratory: arterial blood gases, blood count + differential blood count+ reticulocytes, CRP, PCT, IL-6, urea, creatinine, bilirubin
- UPV parameters (RR, Vt, PEEP, FiO₂, Pplateau, MV)
- need for vasopressors (Y / N)
- renal replacement therapy(Y / N)
- prone position (Y / N)
- ECMO (Y / N)
- medication: antibiotics, antifungal drugs, antiviral drugs; anti-SARS-CoV-2 monoclonal antibodies; immunomodulatory therapy (steroids, immunomodulatory monoclonal antibodies - eg tocilizumab, immunosuppressants); other medicines used to treat COVID-19

Extended monitoring

- indication:
 - ◆ within 36 hours of enrollment in the study
 - ◆ repeated when superinfection is suspected – especially when:
 - ◆ worsening or development of new lung infiltrations
 - ◆ worsening of oxygenation
 - ◆ new purulent secretion from the lower respiratory tract
 - ◆ increase of the level of CRP or PCT, leukocytosis or leukopenia
 - ◆ vasopressors administration or increasing the need for vasopressors
 - ◆ new fever
- repeated examination will be performed no earlier than 3 days from the previous BAL
- the examination will be routinely repeated at 7-day intervals (\pm 1 day) from the previous BAL
- for re-examination, $\text{paO}_2 / \text{FiO}_2$ must be <300 mmHg; if the condition is not met, repeated examination will be performed only if the condition worsens with a decrease in $\text{paO}_2 / \text{FiO}_2$ <300 mmHg

Bronchoscopy and BAL:

- standardized procedure according to the protocol
- bronchoscopic finding
- laboratory diagnostics of BAL fluid:
 - ◆ PCR: pneumonia panel, viral panel, sepsis panel – see below, quantitative monitoring of SARS-CoV
 - ◆ galactomannan (OKMI FN Brno)
 - ◆ cultivation - bacteria and fungi (local microbiology FNUSA / FNB)
 - ◆ albumin, total protein
 - ◆ part of the sample will be frozen for possible further analysis
- Blood:
 - ◆ OKMI FN Brno: galactomannan, beta-D-glucan
 - ◆ biochemistry: ALT, AST, ALP, GMT, LD, CK, ferritin
 - ◆ hematology: D-dimers

Clinical results:

- incidence of bacterial, fungal and viral superinfections
- comparison of PCR diagnostics and pathogens detected in cultivation and antigens
- days without UPV until day 28, days without organ support until day 28
- ICU length of stay
- length of stay in hospital
- mortality (in ICU, hospital, 28-day, 90-day)

End of the monitoring:

- daily and extended monitoring will end after disconnection from mechanical ventilation (CPAP or NIV are not considered as mechanical ventilation)
- participation in the study ends 90 days after enrollment

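### Does dropping the data of patients who wake and refuse consent bias the results enough to need a change to the protocol?

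*Protocol*

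**What the plan says.** Protocol, section Informed consent: because mechanical ventilation is an entry criterion, "patients enrolled in this study will not be able to give informed consent". An independent doctor consents at one hospital and a close relative at the other. The patient's own decision comes later: "After regaining consciousness, patients will be asked for additional informed consent". The consequence of a refusal is fixed: "If they refuse to participate in the study, the data obtained will not be used for analysis". The section does not say that refusals are counted or reported.

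Section Size of the group of patients: "We expect that the University Hospital at St. Anne's enrolls 75 patients and the University Hospital Brno also enrolls 75 patients", which makes 150. No expected mortality or refusal rate is given.

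Section Outcomes: "Primary outcome is incidence and characteristics of superinfections in patients with COVID-19". The secondary outcomes are the diagnostic value of infection and inflammation markers and a comparison of superinfection incidence with a historical cohort. Mortality (ICU, hospital, 28-day and 90-day) appears only under Clinical results, together with "days without UPV until day 28, days without organ support until day 28".

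**The concern.** Only a patient who lives long enough to wake can be removed under this rule. A patient who dies without waking always stays in. Membership of the analysis set therefore depends on the course of the illness, which also determines several reported outcomes. If the removed patients die less often than the whole cohort, all four mortality figures are too high. Ventilator-free and organ-support-free days would plausibly be too low, although that needs refusers to have more such days than average, and late wakers may have few by day 28. Superinfection incidence could move either way.

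This would be a bias and not noise: it does not shrink with enrolment and a confidence interval does not show it. A reader who is not told how many patients refused cannot judge its size.

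**Working it through.** The protocol states no figure that can be reproduced here, so the check is algebra with assumed rates.

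**Inputs.** N = 75 + 75 = 150 (Protocol, Size of the group of patients). Assumed, because the protocol gives none: cohort mortality m, the share r of survivors who refuse, and the share d of refusers who die. R is the number of refusers, set at R = r(1 − m)N, and f = R/N.

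**Bias in mortality.** Analysed mortality = (m − f·d)/(1 − f), so bias = f(m − d)/(1 − f). It is positive only if d < m, zero if d = m and negative if d > m.

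Example with m = 50%, r = 10%, d = 0: f = 0.10 × 0.50 = 0.05; analysed mortality = 0.50/0.95 = 52.6%; bias = 2.6 points.

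| m | r | Refusers of 150 | Analysed mortality, d = 0 | Bias, d = 0 (points) | Bias, d = 25% (points) |
|---|---|---|---|---|---|
| 50% | 5% | 3.75 | 51.3% | 1.3 | 0.6 |
| 50% | 10% | 7.5 | 52.6% | 2.6 | 1.3 |
| 50% | 20% | 15 | 55.6% | 5.6 | 2.8 |
| 40% | 5% | 4.5 | 41.2% | 1.2 | 0.5 |
| 40% | 10% | 9 | 42.6% | 2.6 | 1.0 |
| 40% | 20% | 18 | 45.5% | 5.5 | 2.0 |

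**Is d < m plausible?** Suppose all survivors wake and are asked, a share w of deaths occurs after waking, and refusal is unrelated to later outcome. Then d = w·m/[(1 − m) + w·m], which is below m whenever w < 1. With m from 30% to 60% and w from 0% to 20%, the overstatement is 0.9 to 1.3 points at 5% refusal, 1.8 to 2.6 at 10%, and 4.0 to 5.6 at 20%. Here r applies to everyone who wakes.

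**Scale.** The standard error of a proportion near 50% with 150 patients is √(0.25/150) = 4.1 points. At 5% to 10% refusal the bias stays below this. At 20% it can reach or exceed it.

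**Primary outcome.** Take m = 50%, f = 0.05, d = 0.

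- If 60% of those who die and 40% of survivors have a superinfection, the true incidence is 0.5 × 0.6 + 0.5 × 0.4 = 50.0%. The analysed incidence is (0.5 × 0.6 + 0.45 × 0.4)/0.95 = 0.48/0.95 = 50.5%.
- With the two rates reversed it is (0.5 × 0.4 + 0.45 × 0.6)/0.95 = 0.47/0.95 = 49.5%.

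The shift is about half a point, in a direction that nobody can state in advance. A harsher case has 15 refusers whose incidence differs by 20 points from a cohort rate of 50%. The shift is then 15 × 0.20/135 = 2.2 points, again in either direction.

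**What bounds would add.** Counting all refusers as alive, then all as dead, gives m − f·d to m − f·d + f. The width is f itself: 2.5 points (m = 50%, r = 5%) to 12 points (m = 40%, r = 20%). Given the number of refusers, any reader can work this out.

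**The case for a change.** The best argument for a change is that the protocol, and not the SAP, fixes the exclusion rule, and that the number of refusals is known only if it is recorded as refusals occur. A later SAP might not recover it. The two hospitals also use different entry-consent routes, so refusal could differ between them and a pooled count would hide this. The remedy is cheap, and bounds need only the number of refusers, never their outcomes or clinical data.

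Part of this stands. The selection is real, its likely direction for mortality is upward, and a refusal count per hospital would be useful in the report.

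The rest does not carry a change. The protocol bars the use of refusers' data; it does not bar counting refusals. Each refusal is a distinct event in a consent process that the protocol already requires, and the total equals enrolled minus analysed if nothing else removes patients. Only the protocol was available, and participant flow and sensitivity analyses are ordinarily left to the SAP or the report. The proposed bounds would not alter the point estimate. Their upper end assumes that every refuser dies, although each was alive and conscious when refusing.

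**Conclusion.** No change to the plan follows. The rule is a fair trade-off: respecting a refusal costs a mild selection on survival, and the concern itself does not ask for the rule to be dropped. What is left is a gap in reporting detail that analysts fill as routine, by giving the number of refusals in the participant flow and naming the limitation beside the mortality figures.

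At an assumed 5% to 10% refusal among survivors and 40% to 50% mortality, mortality would be overstated by 0.5 to 2.6 points if 0% to 25% of refusers die, which is less than one standard error. The effect vanishes if refusers die at the cohort rate. Only at about 20% refusal, a rate for which the protocol offers no basis, does it become comparable with the standard error or exceed it. Mortality is neither a primary nor a secondary outcome here. For superinfection incidence, which carries the study's main conclusion and its historical comparison, the shift is about half a point at 10% refusal under the assumed 20-point gap, with no certain direction. All these sizes rest on assumed rates. A refusal rate near 20% or above would call for more caution in reading the mortality figures, but it would not make the rule wrong.

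### Does the statement that group size is irrelevant leave the study without a sound size or a limit on study lavages?

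*Protocol*

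**What the plan says.** Under Size of the group of patients, the protocol ties enrolment to the epidemic and to admissions: "The number of patients enrolled in the study depends on the epidemiological situation". It then gives a forecast, "We expect that the University Hospital at St. Anne's enrolls 75 patients and the University Hospital Brno also enrolls 75 patients", and closes with "The size of the group is not relevant due to character of the study". It states no anticipated rate, target precision, significance level, power, minimum or maximum.

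The outcomes appear under Outcomes and Clinical results. They include overall incidence of superinfection (primary), the "incidence of bacterial, fungal and viral superinfections", the diagnostic value of markers for particular types of superinfection, and a "comparison of the incidence of bacterial and opportunistic superinfections with a historical cohort".

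Under Monitored parameters, "Bronchoalveolar lavage (BAL) is the only procedure that differs from standard care", and "In the study, BAL will be performed early after admission and then in 7-day intervals". Under Informed consent, "patients enrolled in this study will not be able to give informed consent". An independent doctor at one hospital, or a close relative at the other, weighs risks and benefits and consents instead. Patients are asked for their own consent once conscious, and the data of those who refuse are left out of the analysis.

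**The concern.** Two things look wrong. First, an incidence, a set of diagnostic accuracies and a between-cohort difference are all estimated with an error that shrinks as the number of patients grows, so size cannot be immaterial to them. Second, the only design label in the protocol is observational, yet BAL is scheduled by the study in people who lack capacity. The number enrolled therefore sets how many such people are scheduled for a study procedure.

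If the sentence were applied at face value, recruitment could follow the epidemic in either direction. Readers would have no stated precision, and an ethics committee would have no upper bound on exposure.

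**Working it through.** **The plan's own figure.** 75 + 75 = 150. This is a recruitment forecast with no statistical inputs, so only the addition can be reproduced.

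**Overall incidence.** No rate is given, so take 50%, where the interval is widest. The Wilson 95% half-width at 50% reduces to z / (2√(n + z²)), with z = 1.96 and z² = 3.84.

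| Patients analysed | Calculation | Half-width (points) |
|---|---|---|
| 75 | 1.96 / (2√78.84) | 11.0 |
| 100 | 1.96 / (2√103.84) | 9.6 |
| 135 | 1.96 / (2√138.84) | 8.3 |
| 150 | 1.96 / (2√153.84) | 7.9 |
| 300 | 1.96 / (2√303.84) | 5.6 |

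The row for 135 assumes that 10% of 150 later refuse and are removed; the protocol gives no refusal rate. The row for 300 is illustrative only.

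**A type never seen.** The exact upper limit of the two-sided 95% interval is 1 − 0.025^(1/n). This gives 4.8% at n = 75 and 2.4% at n = 150.

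**Marker accuracy.** Assume a type present in 10% of patients and a sensitivity of 80%. With 150 patients there are 150 × 0.10 = 15 cases, and the half-width is 1.96 × √(0.8 × 0.2 / 15) = 20 points (Wilson interval 55% to 93%). With 75 patients there are about 8 cases and the half-width is 28 points. On these assumptions this is the least precise of the outcomes examined.

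**Historical comparison.** The size and rate of the historical cohort are not given. Assume both observed rates are 50%. The Newcombe half-width is then the root of the summed squares of the two Wilson half-widths. For 150 study patients it is:

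- with 75 historical patients, √(7.9² + 11.0²) ≈ 13.6 points;
- with 150, √(7.9² + 7.9²) ≈ 11.2 points;
- with 300, √(7.9² + 5.6²) ≈ 9.7 points.

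Even an unlimited historical cohort leaves 7.9 points, from the study side alone.

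**Study BALs.** Each patient is scheduled for one early BAL, so 150 patients means at least 150 × 1 = 150. Some of these would have been done in usual care, because the protocol says BAL is usual when a suspected lung infection does not respond to antibiotics. The number of additional early BALs is therefore below 150 by an amount the protocol does not give.

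**Reading the sentence in place.** It follows a stated basis (epidemic and admissions) and a stated number (75 per hospital). A team that thought the number truly meaningless would have had little reason to give it. The coherent reading is that the number rests on feasibility and that no formal calculation was made.

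**The case for a change.** The strongest case for a change is that the sentence makes a positive claim, and the claim is false. A SAP can add precision figures, but it does not correct a statement in the protocol. Substitute consent protects each patient but does not limit how many are enrolled. When an invasive procedure is scheduled by the study in people who cannot consent, one would like the total to be bounded, or at least justified. A few sentences giving the feasibility basis, the expected precision and a ceiling of 150 would cost little.

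Much of this stands. The sentence is inaccurate as written, and total exposure moves one for one with enrolment. The remedies are weaker than the criticism:

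- **Ceiling.** It would give up precision (7.9 to 5.6 points if 300 were analysed) to guard against an excess that the protocol nowhere suggests. The protocol names admissions as the constraint, so a shortfall is at least as plausible, and a ceiling does nothing for that. It also changes no individual's risk.
- **Precision promise.** A commitment to at most about 8 points holds only if about 150 patients are analysed. It fails if recruitment ends early (9.6 points at 100) or if refusals are removed (8.3 points at 135).
- **Remaining items.** Expected precision, interval reporting and the size of the historical cohort are details a SAP commonly supplies.

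**Conclusion.** No change to the plan follows. The sentence is a loose way of saying that no formal sample-size calculation was made, and a descriptive observational study whose recruitment is set by an epidemic does not need one. At the expected 150 patients, overall incidence is estimated to within 7.9 points at worst, and rewording the sentence would alter neither the procedures nor the primary result. Analysts will report intervals around whatever number is reached, and these will show the limited precision for rare types and for marker accuracy.

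The conclusion rests on three things: that about 150 patients are analysed (at 75 the half-width is 11.0 points, wider but still usable for description); that the SAP, not seen here, handles interval reporting and describes the historical cohort; and that enrolment stays near the forecast. The figures for marker accuracy and for the historical comparison depend on assumed rates and an assumed historical size. They show only that precision depends on number, which is not in dispute.

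### For patients alive and off the ventilator before day 28, the only described record of vasopressors, renal replacement and ECMO stops before the day-28 window for organ-support-free days closes

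*Protocol*

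**What the plan says.** The protocol's Daily monitoring list contains "need for vasopressors (Y / N", "renal replacement therapy(Y / N", a yes/no item for ECMO, and ventilator settings ("UPV parameters (RR, Vt, PEEP" and others). No other section provides for recording these supports over time. Vasopressors appear once more, under Extended monitoring, but only as a trigger for a repeat examination.

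End of the monitoring then fixes when this record closes: "daily and extended monitoring will end after disconnection from mechanical ventilation". A patient moved to CPAP or NIV counts as disconnected. Participation itself goes on: "participation in the study ends 90 days after enrollment".

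Clinical results lists, among other items, "days without UPV until day 28, days without organ support until day 28". UPV is not spelled out. I read it as invasive mechanical ventilation, because the baseline list names it apart from NIV and HFNO.

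**The concern.** The stop rule follows one organ, the lungs, while the result counts days free of organ support in general. The protocol records vasopressors, renal replacement and ECMO as items separate from the ventilator settings, so it treats them as distinct supports. Any of them may continue or restart once the ventilator is off, and from that point the protocol describes no record of them.

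What is at stake is an error in one direction. Support that nobody records cannot lower the count of support-free days. If the blank days are read as free, the count is too high for exactly those patients who still needed support. The protocol names no source for these days, so the two sites ("enrolls 75 patients and the University Hospital Brno also enrolls 75 patients") could also handle them differently. A SAP can define the result and the treatment of missing days, but it cannot supply data that were never collected.

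**Working it through.** The protocol states no figure for this point, so there is none to reproduce. The check sets the end of data collection against the end of the outcome window.

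**Inputs from the protocol**
- Window for both results: to day 28 (Clinical results).
- Record of vasopressors, renal replacement and ECMO: daily items only (Daily monitoring).
- End of that record: disconnection, on no fixed day and with no 28-day minimum (End of the monitoring).
- End of participation: day 90 (End of the monitoring).

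**Step 1: who is affected.** A patient still ventilated on day 28 has a complete record. The gap concerns only patients alive and disconnected on some day d < 28.

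**Step 2: length of the gap.** If the record runs through day d, the days without a described record number 28 - d. With values of d chosen for illustration:
- d = 10: 28 - 10 = 18 days
- d = 14: 28 - 14 = 14 days
- d = 21: 28 - 21 = 7 days

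**Step 3: possible error in support-free days.** Suppose a survivor is disconnected on day d, stays on some support until day R (d < R ≤ 28), and unrecorded days are counted as free. The record then implies 28 - d free days after disconnection, while the true number is 28 - R. The overstatement is (28 - d) - (28 - R) = R - d. With d = 10 and R = 20 (assumed), that is 18 against 8, an overstatement of 10 days. The ceiling, 28 - d, is reached only with support on every remaining day. A patient with no support after disconnection contributes no error.

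**Step 4: ventilator-free days.** The date of disconnection is enough to derive these unless the patient is reventilated. Reventilation for k days after day d and within the window would overstate them by k. The protocol does not say whether disconnection means the first or the final one, or whether daily monitoring restarts on reventilation.

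**Step 5: does another described item fill the gap?** The other Clinical results that reach past disconnection are ICU stay, hospital stay and mortality. They need dates and vital status only. Support-free days need start and stop dates, or a daily status, for each support. Collecting the former does not provide the latter.

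**The case against.** The strongest reply is that the stop rule names only daily and extended monitoring. Clinical results is a separate block that is not stopped, and participation runs to day 90. Length of stay and mortality are already collected outside the daily list, and the organ-support line states its own window. No sentence says that the result is derived from the daily yes/no items. The data source may also be set in a case report form that is not shown.

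Much of this stands. A reader might infer that the protocol contradicts itself or makes the result unobtainable. It does neither, because the data can be taken from hospital records and, if that is done completely, nothing is lost. What remains is that the one record the protocol describes for non-ventilatory support is expressly ended early, and nothing is put in its place.

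A reader might also infer that hospital records would be incomplete, because the Informed consent section says "Patients enrolled in the study are transported from the entire South Moravian region". That sentence concerns transport in, as a reason why relatives cannot attend to sign. The protocol says nothing about transfer out, so the inference has no support there.

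Finally, a reader might want to put a number on the shift in the cohort mean. That needs the share of patients with support after disconnection and their mean number of such days. The protocol gives neither, so any figure would only reflect the values chosen.

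**Conclusion.** The point holds as a minor gap in data collection, worth considering because it is cheap to close. It applies to patients alive and disconnected before day 28 and chiefly to organ-support-free days. Ventilator-free days are touched only through reventilation.

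For one patient, the error lies between 0 and 28 - d days and can only be upward. It rests on three conditions: support is given after disconnection and before day 28, it goes unrecorded, and the unrecorded days are counted as free. The protocol states none of the three. The size across the cohort is unknown from the document, and it is zero if later status is fully abstracted. The conclusion also takes organ support to mean the supports in the daily list, since the term is not defined in the protocol. Neither result appears under Outcomes as primary or secondary, so the study's main conclusions do not depend on this.

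**What to change.** In End of the monitoring, exempt four items from the stop rule: invasive ventilation, vasopressors, renal replacement and ECMO. Add that their start and stop dates are taken from hospital records to day 28 or death at both sites, whatever the ventilation status and including any reventilation. Days that cannot be obtained are entered as missing, not as support-free. With this wording, neither result depends on whether disconnection means the first or the final one.

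The stop rule can stay as it is for laboratory items, ventilator settings, prone position, medication and extended monitoring. No procedure or treatment changes.

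The cost is limited extra chart abstraction: four items, in at most 75 + 75 = 150 planned patients, all already followed to day 90. Only those alive and disconnected before day 28 need it, and start and stop dates require far fewer entries than a daily form.
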